3.2 Primary Study Endpoints

- 1. The risk of death in AKI group versus controls.
- 2. The risk of CKD progression in AKI group versus controls.

CKD progression will be defined as doubling of serum creatinine, eGFR<15mls/min or the initiation of renal replacement therapy (dialysis or transplantation).

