8.1 Sample Size Determination

The original sample size for the study was based on some assumptions and information published in two studies [10, 11] so in line with the statistical plan in version 1.2 of the protocol, the sample size calculation has been repeated using one year results from the pilot study. The new sample size calculation is based on percentage change in eGFR at one year, a surrogate for subsequent CKD progression (doubling of serum creatinine or progression to CKD stage 5/dialysis). A previous study reported that 21.4% of those who experienced a 20% fall in eGFR at one year progressed to initiation of RRT [18]. Results from the pilot study have shown that 13 patients experienced such a decline in eGFR at one year in the control group as compared to 29 in the AKI group. Therefore, the estimated proportion in the control group that will progress to a doubling of serum creatinine or progression to CKD stage 5 is 2.02% as compared to 4.41% of the AKI group. Assuming a 5% significance level and 80% power this means that 430 patients will be required per group. Assuming a drop-out rate of 26% then a total of 542 patients will be required in each group.

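### The 2.02% and 4.41% behind the sample size are RRT-only rates in one-year eGFR decliners, labelled as whole-group rates of the renal endpoint; the net effect on power is unknown

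*Protocol*

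**What the plan says.** Protocol section 3.2 sets the renal primary endpoint: "CKD progression will be defined as doubling of serum creatinine, eGFR<15mls/min or the initiation of renal replacement therapy" (dialysis or transplantation).

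Section 8.1 says the revised sample size is "based on percentage change in eGFR at one year, a surrogate for subsequent CKD progression". Its conversion figure comes from a published cohort: "21.4% of those who experienced a 20% fall in eGFR at one year progressed to initiation of RRT". The pilot supplies the counts: "13 patients experienced such a decline in eGFR at one year in the control group as compared to 29 in the AKI group". From these the section concludes that "the estimated proportion in the control group that will progress to a doubling of serum creatinine or progression to CKD stage 5 is 2.02"%, giving the pair "2.02% as compared to 4.41% of the AKI group".

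Those two rates, with 5% significance and 80% power, lead to 430 per group, and a 26% drop-out allowance raises this to 542. Section 8.1 gives no pilot denominators, no time horizon for the 21.4%, and no progression rate for participants without a one-year fall. Section 5 follows renal function to 10 years.

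**The concern.** Within one paragraph the outcome changes. The conversion figure concerns starting RRT. The result is labelled as creatinine doubling or CKD stage 5, which is in substance the composite of section 3.2. RRT is one of three components of that composite, so an RRT-only conversion does not give its rate.

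The population changes too. The 21.4% applies to people whose eGFR fell by 20%, while the result is presented as a proportion of the whole group. A whole-group rate needs a contribution from people without a fall, and none is mentioned.

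In a two-proportion calculation the two rates fix both the effect and the variance. If they belong to another outcome, any power figure built on them describes that outcome, not the one the log-rank test and Cox model in section 8.2 will analyse.

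**Working it through.** **Inputs.** From section 8.1: 21.4% conversion, 13 control and 29 AKI decliners, rates of 2.02% and 4.41%, 430 and 542 per group, 26% drop-out. The endpoint is from section 3.2. Assumed, because the protocol gives neither: the composite risk after a fall, r, and without a fall, q.

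**1. How the printed rates arise.** Dividing by the conversion rate gives the implied decliner shares:
- control: 2.02 / 21.4 = 9.44%; 13 / 0.0944 gives about 138 patients
- AKI: 4.41 / 21.4 = 20.61%; 29 / 0.2061 gives about 141 patients

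Forward check: 0.214 × 13/138 = 2.02%. 0.214 × 29/141 = 4.40%, or 4.41% if the share is first rounded to 20.6%. The denominators are inferred, and the division presumes no second term, so this shows consistency rather than proof. Whole-number denominators of similar size in the two groups reproduce both rates to within rounding, so the simple product is the natural reading.

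**2. What the product leaves out.** The rate for a group with decliner share d is

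P = d × r + (1 − d) × q.

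The plan uses r = 21.4% (RRT only) and, as inferred, q = 0 for about 91% of controls and 79% of AKI patients. The planned ratio, 4.41 / 2.02 = 2.18, is then just the ratio of decliner shares, 20.61 / 9.44.

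**3. Power on the plan's own rates.** A two-sided 5% unmatched two-proportion test (normal approximation) of 2.02% v 4.41% has 51% power at 430 per group. About 854 per group are needed for 80%, so the stated 430 is not reproduced. That is a separate fault; here 51% serves only as the reference.

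**4. Two-term rates, with r and q each equal in both groups.** Power is at 430 per group.

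| r (after a fall) | q (no fall) | Control | AKI | Ratio | Power |
|---|---|---|---|---|---|
| 21.4% | 0 | 2.02% | 4.41% | 2.18 | 51% |
| 21.4% | 0.5% | 2.47% | 4.81% | 1.94 | 45% |
| 21.4% | 1% | 2.93% | 5.20% | 1.78 | 39% |
| 21.4% | 2% | 3.83% | 6.00% | 1.57 | 31% |
| 30% | 0 | 2.83% | 6.18% | 2.18 | 66% |
| 30% | 2% | 4.64% | 7.77% | 1.67 | 48% |
| 40% | 0 | 3.78% | 8.24% | 2.18 | 79% |
| 40% | 2% | 5.59% | 9.83% | 1.76 | 65% |
| 50% | 0 | 4.72% | 10.30% | 2.18 | 88% |
| 50% | 2% | 6.53% | 11.89% | 1.82 | 78% |

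Example, r = 21.4% and q = 2%: control 0.0944 × 0.214 + 0.9056 × 0.02 = 3.83%; AKI 0.2061 × 0.214 + 0.7939 × 0.02 = 6.00%.

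Raising r lifts both rates and the power. Raising q dilutes the ratio and lowers the power.

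**5. Conditional risks that differ by group.**
- r = 21.4% in both groups, q = 0.5% control and 2% AKI: 2.47% v 6.00%, ratio 2.43.
- q = 0 in both groups, r = 21.4% control and 30% AKI: 2.02% v 6.18%, ratio 3.06.
- With equal r, the ratio passes 2.18 once the AKI risk without a fall exceeds 2.18 × 0.9056 / 0.7939 = 2.49 times the control risk.

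**6. At the fixed enrolment.** 542 × 0.74 = 401 evaluable per group. Power there is 48% on the plan's rates, 29% at r = 21.4% and q = 2%, and 85% at r = 50% and q = 0.

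**The case against.** The protocol says openly that one-year eGFR change is a surrogate, and planning on a surrogate is an accepted approximation. That stands as a defence of using the 20% fall. It does not cover presenting an RRT rate as the proportion reaching the composite, which the text does without qualification.

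The zero risk for non-decliners is inferred from undisclosed denominators. This is correct, and the point is limited accordingly. The RRT-for-composite substitution is on the page and does not depend on it.

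A reader might infer that 2.18 is the largest possible ratio, so that the planned effect must be overstated. The documents do not support this. It requires risk given decline status to be equal in the two groups. The plan uses one figure for decliners in both groups and says nothing about non-decliners. Whether AKI carries risk beyond its effect on one-year eGFR is close to the study's own question.

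A reader might also infer that this fault makes the study underpowered. That does not follow either. Counting the missing components raises the rates, and with a high enough risk after a fall 430 per group would suffice. The 51% reference reflects the mismatch between 430 and about 854, not this input.

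**Conclusion.** The point holds in limited form. The 2.02% and 4.41% are the expected shares of each whole group who have a 20% one-year fall and then start RRT. They are not the rates of the endpoint in section 3.2. Leaving out the non-RRT components understates the absolute rates. Giving non-decliners no risk, if that was done, inflates the ratio when conditional risks are equal across groups, and otherwise may not.

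The net direction for power is unknown. With risks after a fall of 21.4% to 50% and without one of 0 to 2%, equal in both groups, power at 430 per group runs from about 31% to about 88%. These limits are assumptions, and the calculation ignores the matching and the timing of events. Correcting only the arithmetic from the rates to 430 would leave a correct calculation for a different outcome, so the two corrections belong together.

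**What to change.** In section 8.1, give for each group P(fall) × P(composite | fall) + P(no fall) × P(composite | no fall), using the composite of section 3.2. State the pilot denominators, low and high values for the conditional risks, and the time horizon they refer to. Restate power as a range at the fixed 542 enrolled per group (about 401 evaluable after 26% drop-out), together with the correction of the 430 figure.

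If composite risks cannot be obtained, relabel 2.02% and 4.41% as the proportion of all participants in each group expected to have a 20% one-year eGFR fall and then start RRT. Say that this is a proxy for the primary renal endpoint and not its rate. The label must not read as RRT among those with a fall, because that figure is 21.4%. If 2.18 is described as an upper limit, the equal-conditional-risk assumption must be stated beside it.

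The cost is a few lines of protocol text and a recalculation, with no change to recruitment. The downside is that the stated power becomes a range and may be less favourable.

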4.2.1 Group A – main study

All patients with AKI will be screened for inclusion into the study, as well as those patients tested for possible AKI but who did not sustain it. Patients will not be approached until at least two months after they have recovered from their acute illness, by which time the majority of patients will have returned home.

Recruitment, matching and consent

Patients who meet the inclusion criteria will be contacted via post and invited to participate. The control group will be matched to AKI patients on a 1:1 basis in terms of baseline eGFR (within the same CKD stage but as closely as possible) and age \pm 5yrs. In addition they will be recruited from a similar inpatient setting. Due to the proposed three year follow up, patients over 85yrs will be excluded as the reduced life expectancy due to age alone in these patients may affect the outcome measures of mortality.

Potential subjects will receive a letter of invitation along with a comprehensive patient information sheet. Interested patients will be asked to telephone a number at the Royal Derby Hospital during which patient identity will be affirmed using standard data protection questions. After confirmation that the patients are in possession of the information required to provide valid consent, they will be sent a consent form that they will sign and return in a pre-paid envelope, retaining a copy for themselves (see section 4.2.2 for more details of the consent process). If patients do not wish to participate they will be asked to confirm this by telephoning the same number. This methodology has been piloted and has been shown to be very successful in more than 300 patients to date, with very positive feedback from participants.

Each patient will be assigned a unique study number that will be used to identify all data collected for the study. This will be allocated upon recruitment. A key of patient identity and study numbers will be kept on a password-protected Trust server in a password-protected file. Any information passed onto the Medical Research Information Service will be in encrypted form. A recruitment log will be maintained and the patients' GPs will be informed of their participation in the study by letter.

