8.3 Subject Population(s) for Analysis

All patients will be included in the analyses described above except for those in the control group who subsequently sustain AKI during the study period, who will be excluded. Depending on the frequency of this occurrence a separate 'intention to treat' secondary analysis may be performed. Data from patients who withdraw (and give consent) or who die will be included until the date of withdrawal or death.

9 Safety and Adverse Events

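### The drop-out allowance appears to multiply by 1.26 instead of dividing by 0.74, so 542 per group leaves about 401 patients, not the 430 required

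*Protocol*

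**What the plan says.** Section 8.1 of the protocol sets the sample size in two steps. The first gives the number needed for analysis: "Assuming a 5% significance level and 80% power this means that 430 patients will be required per group". This rests on expected proportions reaching the renal endpoint, where the control figure "is 2.02% as compared to 4.41% of the AKI group". The second step allows for attrition: "Assuming a drop-out rate of 26% then a total of 542 patients will be required in each group".

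The Study Summary gives 1084 subjects, which is 2 × 542, in keeping with the 1:1 matching in section 4.2.1. Section 8.1 states no inflation formula, and no further allowance appears elsewhere in the protocol.

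**The concern.** A drop-out rate is a fraction of the patients recruited. To finish with n patients when a fraction d is lost, one recruits n/(1 − d). Multiplying n by (1 + d) instead treats d as a fraction of those who remain. It always recruits too few, and the shortfall grows with d. At 26% it is no longer a matter of rounding.

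What is at stake is the headline recruitment target. As stated, 1084 recruits do not deliver the sample the plan says it needs at the attrition the plan itself assumes. CKD progression is one of the two primary endpoints (section 3.2), its expected proportions are low, and follow-up runs to ten years (section 3.1), so the attrition allowance matters. If the same rule is used in a later recalculation, the error will recur with a larger base number.

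**Working it through.** **Inputs**, all from section 8.1 unless noted:

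- required per group: n = 430
- drop-out rate: d = 0.26
- recruited per group: 542; total 1084 (Study Summary)
- proportions: 0.0202 (control) and 0.0441 (AKI)
- significance level 5%; the protocol does not state sidedness, and two-sided is assumed here

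**Reproducing the plan's figure.** n × (1 + d) = 430 × 1.26 = 541.8, rounded up to 542. Doubling gives 1084. The match is exact, but because no formula is printed, the use of 1.26 is an inference.

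**The number that keeps 430.** n / (1 − d) = 430 / 0.74 = 581.1, rounded up to 582 per group. The total is 2 × 582 = 1164, which is 1164 − 1084 = 80 more than stated.

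**What 542 delivers at 26% drop-out.** 542 × 0.74 = 401.1, about 401 per group. The shortfall is 430 − 401 = 29 per group, or 58 in total, and 29/430 = 6.7%.

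**The drop-out rate that 542 does cover.** 1 − 430/542 = 0.207, or 20.7%. Put another way, 542 − 430 = 112 losses, which is 26.0% of 430 but only 20.7% of 542.

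**Effect on power.** With the pooled two-proportion formula,

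power = Φ{ [ |p1 − p2| √n − 1.96 √(2 p̄ (1 − p̄)) ] / √( p1(1 − p1) + p2(1 − p2) ) },

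where |p1 − p2| = 0.0239, p̄ = 0.03215, √(2 p̄ (1 − p̄)) = 0.2495 and the denominator is 0.2489:

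| Patients per group | Two-sided power |
|---|---|
| 430 | 51% |
| 401 | 48% |

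The drop-out step therefore costs about 3 points. The low starting level has another cause: the same formula gives 854 per group for 80% power, so 430 does not follow from the stated proportions.

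The isolated cost is similar if the plan's claim of 80% power at 430 is taken at face value. The standardised effect is then 1.96 + 0.84 = 2.80. Scaling by √(401/430) = 0.966 gives 2.70, and Φ(2.70 − 1.96) = Φ(0.74) = 77%.

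**The error is independent of the 430.** If 430 were replaced by 854 and the same rule kept, the target would be 854 × 1.26 = 1076.04, so 1077 per group. The number needed would be 854 / 0.74 = 1154.05, so 1155.

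**The case against.** The strongest counter-argument is that a patient who drops out is not wholly lost. Section 8.3 says: "Data from patients who withdraw (and give consent) or who die will be included until the date of withdrawal or death". The primary analyses are log-rank and Cox (section 8.2), so such patients are censored and still contribute follow-up. Outcomes do not rest on study visits alone either. The renal database identifies chronic renal replacement therapy, the national tracking service follows survival to ten years (section 3.1), and withdrawn patients are asked to allow later clinical events and GP kidney function results to be collected (section 4.3.2). On this view, 401 is the number with complete follow-up, and the information lost is less than 29 patients per group.

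That is fair as to the practical loss, and it stands. It does not reconcile the figures. The calculation in section 8.1 compares proportions and makes its own allowance for drop-out, and that allowance is the wrong size for the rate given. Two provisions also work the other way. Participants who decline retention have their data deleted (section 4.3.2). Controls who later sustain AKI are excluded (sections 4.3 and 8.3), and the protocol does not say whether the 26% covers them.

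A second objection is that 430 is itself wrong, so 582 and 1164 are not real targets. That is correct: both are conditional on 430. The inflation error remains whatever base number is used.

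A third is that 3 points of power do not decide whether the study can answer its question. That also stands. The case for correction is that a sample-size figure on which the study relies is misstated, not that this step alone leaves the study underpowered.

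**Conclusion.** The concern holds. The figures 430, 26% and 542 are mutually inconsistent, however 542 was reached, and the Study Summary total of 1084 carries the inconsistency. At 26% drop-out the target leaves about 401 per group, 29 short per group and 58 in total (6.7%). Meeting 430 would need 582 per group. The cost in two-sided power is about 3 points, from 51% to 48% at the plan's own proportions.

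This reads the drop-out rate as a fraction of recruits and counts drop-outs as not contributing to a comparison of proportions. Censored follow-up and record linkage would reduce the loss in the time-to-event analyses by an amount that cannot be calculated from the protocol. The larger shortfall, that 430 does not give 80% power for the stated proportions, is a separate matter. Correcting the drop-out step alone would not restore 80% power.

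**What to change.** Correct the last sentence of the calculation in section 8.1 and make the Study Summary agree. Either of these statements would be accurate:

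- 1084 recruits (542 per group) are expected to leave about 401 per group at 26% drop-out, with the power for that number stated; or
- 542 per group protects 430 only if drop-out does not exceed 20.7%.

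Section 8.1 should print the formula, n/(1 − d), and use it in any later recalculation. It should also say whether the 26% includes controls excluded for later AKI. The correction is best made together with the review of the 430, because 582 and 1164 lapse once that number changes.

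The cost is a corrected sentence in section 8.1 and a matching entry in the Study Summary. No extra recruitment and no change to design, endpoints or analysis is needed to make the statement true. The price is that the stated number retained, and the power with it, becomes slightly less favourable.

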8.2 Statistical Methods

Statistical analysis will be performed using SPSS v19.0 and Stata v11. Descriptive statistics will be used to summarise baseline variables in AKI and control groups. Univariate parametric or non-parametric analysis will be done to compare the two groups at baseline. Kaplan-Meier curves will be constructed to compare the primary endpoints, renal end-point and mortality between the two groups using the Log-Rank test. A Cox proportional hazard model will be used to test the effect of AKI on primary endpoints adjusted for age, gender, (race if possible), co-morbidity (diabetes, hypertension, malignancy, cardiovascular disease), baseline renal function, proteinuria, requirement for acute dialysis and multiple episodes of AKI. Conditional logistic regression will be performed for exploring the effect of AKI matched patients and secondary outcomes on the proportion of patients with CKD progression and on their mortality status at 12 months. Participants with cirrhosis will be included in the main analysis, but their co-morbid conditions will be accounted for in the statistical analysis.

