1.1 Background

Acute Kidney Injury (AKI) is very common in acutely ill patients and is associated with longer, more complicated hospital stays and worse patient survival. The RIFLE criteria and subsequent modification by AKIN now provide a widely accepted definition of AKI that is predictive of short term outcomes [1]. Mortality progressively increases with severity of AKI; the mortality rate of critically ill patients on the intensive care unit (ICU) who receive renal replacement therapy (RRT) ranges between 50-80% [1]. There is now an increasing recognition that episodes of AKI may also have profound longer term sequelae. There are some studies suggesting that AKI leads to chronic kidney disease (CKD) and increases the risk of end-stage renal failure requiring dialysis [2-7]. Clearly this is very important as CKD and dialysis in particular have major effects on patient well-being and symptomatology; it follows that survivors of AKI may also have a worse long term survival rate as compared to those who do not sustain AKI [3, 8, 9]. There are also huge health economic implications bearing in mind the annual cost of haemodialysis for just one patient is £30,000.

However, the majority of studies in this area are retrospective and many include only specific patient groups such as ICU patients who required RRT, those undergoing surgical procedures or following coronary angioplasty. Furthermore, several of the published studies are historical and do not use the current diagnostic criteria for AKI [2, 4, 10, 11]. It is therefore unclear as to whether an association really exists between AKI and long term outcomes in a general hospitalised population who form the largest group of patients sustaining AKI. In addition, it remains to be seen whether associations between AKI and outcomes are causal, and whether patients at higher risk of subsequent adverse outcomes can be identified to allow targeting of follow up and more intensive management to those with the greatest clinical need. This will also inform the design of future interventional research studies.

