3.1 General Design

This is a long-term longitudinal observational case-control study. Basic blood tests to include measuring renal function, haemoglobin, albumin and proteinuria will be measured at study entry as well as 1 year, 3 years, 5 years and 10 years after AKI (approximately 9months, 33months, 57 months and 117 months after recruitment). Samples will also be collected and stored at each of these time points for subsequent biomarker measurement; these will consist of inflammatory markers (IL-6, high sensitivity CRP) and plus a panel of biomarkers of tubular injury (to include NGAL and IL-18). Included patients will have baseline demographics, co-morbidity and acute illness details extracted from the hospital PAS system. AKI stage and baseline renal function (that prior to sustaining AKI) will be extracted from the electronic AKI reporting system currently in clinical use at the Royal Derby Hospital. This novel system identifies all episodes of AKI from every inpatient location and also reports severity as per AKIN staging; the diagnostic accuracy of this system has been confirmed and reported previously [16].

Patients receiving acute dialysis during the episode of AKI will be identified from renal unit and intensive care unit databases; the renal database (Vitaldata) will be used to identify those patients who subsequently require chronic renal replacement therapy (RRT). The Medical Research Information

Service (MRIS, an arm of the NHS Information Centre) will be used to accurately track survival data of participants to **ten** years after the AKI episode.

A pilot study, specifically designed to test this methodology and recruitment process is currently underway, and demonstrates that the proposed recruitment, consent and matching processes are both practicable and feasible (recruitment rate ~20%, with approximately 15 participants recruited per week).

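### With deaths in effect censored, the Kaplan-Meier curves for the renal endpoint overstate the absolute risk of CKD progression; cumulative incidence with death as a competing event should be shown instead

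*Protocol*

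**What the plan says.** Section 3.2 of the protocol names two primary endpoints, death and CKD progression. The second is worded as a risk: "The risk of CKD progression in AKI group versus controls". Its definition contains no death component: "CKD progression will be defined as doubling of serum creatinine, eGFR<15mls/min or the initiation of renal replacement therapy (dialysis or transplantation".

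Section 8.2 fixes the analysis: "Kaplan-Meier curves will be constructed to compare the primary endpoints, renal end-point and mortality between the two groups using the Log-Rank test". A Cox model for the primary endpoints follows. No cumulative incidence estimate, competing-risk model or composite of renal event and death is named.

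Section 8.3 sets out how deaths are handled: "Data from patients who withdraw (and give consent) or who die will be included until the date of withdrawal or death". Death and withdrawal are treated alike.

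Under section 3.1, renal function is "measured at study entry as well as 1 year, 3 years, 5 years and 10 years after AKI", and the national information service is used to "accurately track survival data of participants to" ten years. Section 4.1.1 admits patients up to age 85. On mortality, section 1.1 says that "survivors of AKI may also have a worse long term survival rate". The protocol gives no mortality rate for either group.

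**The concern.** A patient who withdraws can still progress to the renal endpoint later; a patient who has died cannot. If both are removed from the risk set at the date they leave, the Kaplan-Meier estimator in effect gives the dead the same future renal risk as those still alive. Its complement then estimates the risk in a hypothetical population without death, not the share of patients who will actually progress.

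Section 3.2 asks for a risk in each group, and the natural way to read that from the planned analysis is off the curves. Follow-up of ten years in recently hospitalised adults up to age 85 leaves room for many deaths. What is at stake is the absolute renal risk in each group, and the risk difference and risk ratio derived from it. If mortality differs between the groups, the relative overstatement differs too.

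**Working it through.** **The plan's own figures.** The protocol gives no ten-year Kaplan-Meier estimate to reproduce. The only renal proportions are in section 8.1: 2.02% (controls) and 4.41% (AKI). They are used here as 1-KM at ten years; that time point is an assumption, because section 8.1 attaches none. The sample size of 430 per group in section 8.1 plays no part in this check. It is not reproduced from these proportions (the pooled two-sided formula gives 854), but that is a separate matter.

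**Other inputs.**
- Follow-up T = 10 years (section 3.1).
- Ten-year deaths: not in the protocol. Assumed range, controls/AKI: 20/20%, 20/30%, 30/30%, 30/45%, 40/60%, 50/50%.
- Constant cause-specific hazards: assumed.

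**Formulas.** With renal hazard r and death hazard d:
- 1-KM = 1 − exp(−rT), so r = −ln(1 − 1-KM)/T
- d = −ln(1 − deaths)/T
- Cumulative incidence = r/(r + d) × [1 − exp(−(r + d)T)]

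**Worked case, deaths 30% and 45%.**
- Controls: r = −ln(0.9798)/10 = 0.00204; d = −ln(0.70)/10 = 0.03567. Cumulative incidence = 0.00204/0.03771 × (1 − 0.9798 × 0.70) = 1.70%.
- AKI: r = −ln(0.9559)/10 = 0.00451; d = −ln(0.55)/10 = 0.05978. Cumulative incidence = 0.00451/0.06429 × (1 − 0.9559 × 0.55) = 3.33%.
- Relative excess of 1-KM: 2.02/1.70 gives 19% (controls); 4.41/3.33 gives 33% (AKI).
- Risk difference: 4.41 − 2.02 = 2.39 points by 1-KM; 3.33 − 1.70 = 1.63 points by cumulative incidence.
- Risk ratio: 2.18 by 1-KM; 1.96 by cumulative incidence.

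**Over the assumed range** (1-KM is 2.02% and 4.41% throughout, risk ratio 2.18):

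| Deaths, controls/AKI | Cumulative incidence, controls | Cumulative incidence, AKI | Relative excess of 1-KM, controls/AKI | Risk ratio |
|---|---|---|---|---|
| 20/20% | 1.81% | 3.96% | 12% / 11% | 2.18 |
| 20/30% | 1.81% | 3.71% | 12% / 19% | 2.05 |
| 30/30% | 1.70% | 3.71% | 19% / 19% | 2.18 |
| 30/45% | 1.70% | 3.33% | 19% / 33% | 1.96 |
| 40/60% | 1.58% | 2.90% | 28% / 52% | 1.83 |
| 50/50% | 1.46% | 3.19% | 38% / 38% | 2.19 |

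1-KM is too high in every row. In absolute terms the excess is about 0.2 to 0.6 points in controls and 0.5 to 1.5 points in AKI. The ratio moves only when mortality differs between the groups.

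**What the choice of test targets.** Take an assumed renal hazard of 0.5% per year in both groups, with deaths at 5% per year in controls and 8% in AKI. Then 1-KM is 1 − exp(−0.05) = 4.88% in both groups. Cumulative incidence is 0.005/0.055 × (1 − exp(−0.55)) = 3.85% in controls and 0.005/0.085 × (1 − exp(−0.85)) = 3.37% in AKI. The log-rank test has no renal difference to find here. A test on cumulative incidence does, and in favour of AKI, only because more AKI patients die first.

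**The case against.** The strongest reply is that the planned comparison is sound. With deaths censored, the log-rank test and the Cox model compare cause-specific hazards. That is a legitimate target, and it suits the question in sections 1.1 and 2 about the effect of AKI on progression. This stands. A reader might infer that the renal tests are invalid, or that Gray's test should replace the log-rank test; neither follows. The equal-hazard example shows that replacing the test could make AKI look protective for the kidney merely through higher mortality.

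Second, a reader might infer that the distortion is unequal by design, or that deaths are bound to far outnumber renal events. The protocol supports neither as fact. Section 1.1 says only that survival after AKI may be worse, mortality is itself one of the primary questions, and no death rate is given.

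Third, section 3.3 also lists the proportion reaching the renal endpoint and the mortality at each time point. That is partial mitigation: a crude proportion keeps the dead in the denominator but does not handle loss to follow-up. The conditional logistic regression in section 8.2 stops at 12 months. Neither supplies a ten-year risk that allows for death.

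Fourth, further competing-risk estimates could be left to a statistical analysis plan, which is not shown here. True, but section 8.2 does not leave the estimator open: it names Kaplan-Meier for this endpoint. Finally, section 8.3 does not use the word censoring. It is inferred from the rule that data run only to death, combined with an endpoint that excludes death; within a Kaplan-Meier renal analysis no other reading fits well.

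**Conclusion.** The point holds for absolute risk only. Kaplan-Meier curves for the renal endpoint, with deaths in effect censored, overstate the risk of CKD progression in each group. The direction does not depend on the assumed death rates; the size does. Over the assumed range the relative overstatement is 11% to 52%, which is modest in absolute terms at the protocol's low renal proportions and larger if the ten-year renal risk is higher. The relative overstatement is greater in the AKI group only if its mortality is higher; with equal mortality the risk ratio hardly changes. These sizes rest on constant hazards, on assumed mortality and on reading 2.02% and 4.41% as ten-year values. The change is worth making, but the planned hazard comparison is not undermined.

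**What to change.** In section 8.2:
- Present absolute renal risk as Aalen-Johansen cumulative incidence with death as a competing event, instead of 1-KM.
- Keep the log-rank test and Cox model for the renal endpoint, label both cause-specific, and show the hazard of death beside them.
- Keep Kaplan-Meier and log-rank for mortality.
- Gray's test or a Fine-Gray model may be added as a supplement, but should not replace the cause-specific comparison.

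The cost is a small amount of extra analysis. Survival is already tracked to ten years under section 3.1, so no new data are needed.
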